#### **Intervention, tests or procedures:**

Regardless of group assignment, all participants will be expected to engage in 1-hr exercise sessions, 2 d/wk for 6 months. The basic training program for all three study arms is a functional strength training program based on recommendations for improving muscle strength in adults[41] and our prior studies in cancer survivors. For safety reporting purposes, a monthly Adverse Event Survey will be sent electronically or completed over the phone. More details about this survey can be found under section 19.1 Monitoring Plan.

#### **Follow up tests and procedures:**

After the completion of the 6 month exercise intervention, all couples will be followed for an additional 6 months after formal training stops. Couples may wish to maintain their exercise habits or participate in shared activities other than exercise after formal training stops and we will not discourage them from doing so. To provide couples in supervised programs a resource to continue to engage in exercise after supervised training stops we will provide them with a DVD of their programs to use at home.

All biomarkers of inflammation and cardiovascular health will be measured from blood obtained from participants by the Oregon Clinical Translational Research Institute (OCTRI), following established protocols. Participants will be asked to fast and abstain from smoking cigarettes, drinking alcohol or drinking caffeinated beverages for 12 hours before the blood is drawn.

The total duration of an individual subject's participation in the study is 12 months. Certain data (questionnaires and adverse events follow-up) may be collected after this 12-month period, when a participant is off study, using IRB-approved language. With participant approval, we may contact a patient's provider to confirm cancer history.

When participants drop out of the research their data will be retained for analysis. If a participant becomes ineligible during the study s/he will be withdrawn by the investigator and data will no

longer be collected; however, in these cases the participant would be allowed to continue in the study exercise program as long as the reason for ineligibility does not contraindicate exercise participation.

*Drop out of one exercise partner in Exercising Together arm:* If one partner of a couple is unable or unwilling to continue exercise training, any data collected on them prior to their withdrawal will be used for purposes of this research. Data will be continued to be collected on the other partner and they will be allowed to continue in the exercise program. If needed their program will be adapted so that it can be performed independently.

The investigator may choose to withdraw a participant without their consent if his/her health changes and the study is no longer in their best interest, if new information becomes available, if he/she does not follow the study rules, and/or if the study is stopped by the IRB.

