#### **Six-Month Follow-Up Period**

To evaluate the persistent effects of *Exercising Together* on individual and relationship health, all couples will be followed for an additional 6 months after formal training stops. Couples may wish to maintain their exercise habits or participate in shared activities other than exercise after formal training stops and we will not discourage them from doing so. To provide couples in supervised programs a resource to continue to engage in exercise after supervised training stops we will provide them with a DVD of their programs to use at home. During the last month of supervised training we will prepare participants for the transition to unsupervised training with discussions about behavioral strategies to stay active. We will assess participation in exercise and shared activities at 9 & 12 months and consider these behaviors in analysis for Aim 3 (see **Analysis Plan**). We will also repeat all measures at month 12 in order to better assess the residual effects of *Exercising Together* among couples that do or do not continue to exercise or engage in shared activities in the follow-up period.

**Participant safety.** None of our participants have dropped out of a study due to an injury related to exercise training; however, as with any study in older adults, exercise adherence has been affected by minor musculoskeletal complaints that usually stem from pre-existing orthopedic conditions. We will reduce the risk of injury and symptoms that might limit exercise adherence by: 1) required physician clearance for every participant and 2) monitoring and early care of musculoskeletal symptoms. If a survivor develops metastatic disease during the study his/her data from the point of the diagnosis will be considered separately, but s/he could continue in the study program with physician clearance.

**Participant Incentives:** Remuneration will be provided to couples based on completion of each study related activity as outlined in the table below, at each of the four main time points (baseline, 3-months, 6-months, and 12-months).

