#### **5.0 INCLUSION/EXCLUSION CRITERIA**

##### **Inclusion Criteria: *Survivors Only:***

- Histologically confirmed PC, BC or CRC without evidence of metastatic disease (confirmed by self-report on Health History Questionnaire. In the case a participant isn't able to confirm this criterion, a letter will be sent to his or her physician)
- Three years or less from diagnosis date, by month and year, at time of enrollment (confirmed by self-report on Health History Questionnaire. In the case a participant isn't able to confirm this criterion, a letter will be sent to his or her physician)
- Completed treatment (e.g., surgery, radiation and/or chemotherapy)  $\geq$ 6 weeks prior to enrollment. Concurrent adjuvant hormone therapy is permitted and must have been initiated  $\geq$  6 weeks prior to enrollment. For prostate cancer, Androgen Deprivation Therapy (ADT) may constitute primary treatment and must have been initiated  $\geq$  6 weeks prior to enrollment. For breast cancer, hormone therapy may constitute primary treatment and must have been initiated  $\geq$  6 weeks prior to enrollment. (confirmed by self-report on Health History Questionnaire. In the case a participant isn't able to confirm this criterion, a letter will be sent to his or her physician)
- Co-residing with an intimate partner or spouse who is willing to participate (confirmed by self-report on Health History Questionnaire)

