##### **Exclusion Criteria: *Survivors and Spouses/Partners:***

- Cognitive difficulties that preclude answering the survey questions, participating in the exercise classes or performance tests, or providing informed consent as determined by the professional opinion of the Principal Investigator, [name].
- A medical condition, movement or neurological disorder, or medication use that contraindicates participation in moderate intensity exercise. Specific contraindications include the following: declared pregnancy, poorly controlled diabetes, recent cardiac event, neuromuscular disease, untreated orthostatic hypertension, recent surgery, acute hernia, acute rheumatoid arthritis, severe memory disorders, severe balance disorder, inability to ambulate (use of an assistive device permitted), inability to stand for 3 minutes,

severe hearing or vision problem. (For Survivor: Confirmed by physician clearance; For Spouse/Partner: must answer 'No' to American College of Sports Medicine pre-participation screening questions [103]. If spouse/partner answers 'Yes' to either question they will be considered eligible upon physician clearance. Physician clearance may also be requested at the discretion of the Principal Investigator. For either: absence of pregnancy in persons who could possibly be pregnant but have not declared a pregnancy at screening, will be further screened with a pregnancy test administered at each testing visit, unless only participating remotely.)

- Knowingly unable to attend >75% of the intervention classes due to conflict with the designated time of day, days of the week, and/or location for the exercise class which they initially enrolled. (Confirmed by documentation in the Case Report Form titled "CRF - Participant Contact Info\_Exercising Together")
- Not fluent in English and therefore incapable of answering survey questions, participating in class, following directions during performance testing, and providing informed consent when English is the language used. (Confirmed by documentation in the Case Report Form titled "CRF - Participant Contact Info\_Exercising Together" or the professional opinion of the Principal Investigator, [name].)

Ancillary study: Participants recruited for the ancillary study will not be screened with a pregnancy test due to remote participation.

Ancillary study: To expand the pool of eligible participants, we will include survivors with a longer interval since diagnosis, as below.

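### Section 8.0 stops outcome collection for randomised participants who become ineligible, creating avoidable missing data that the ITT analysis handles only under MCAR or MAR

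*Combined protocol and SAP*

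**What the plan says.** **Stop rule.** Section 8.0, Follow up tests and procedures, begins the rule with "If a participant becomes ineligible during the study s/he will be withdrawn by the investigator and data will no", so that collection ends at that point. On training, the second half of the sentence reads "longer be collected; however, in these cases the participant would be allowed to continue in the study exercise program", provided that the reason for ineligibility does not rule out exercise.

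**Metastatic disease.** Absence of metastases is an inclusion criterion in section 5.0: "Histologically confirmed PC, BC or CRC without evidence of metastatic disease". For a survivor who develops metastases during the study, section 3.0 (Participant safety) says "his/her data from the point of the diagnosis will be considered separately, but s/he could continue in the study program with physician clearance".

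**Scope after randomisation.** The section 8.0 schedule of events places eligibility at screening only. Section 5.0 repeats one check: a person who could be pregnant "will be further screened with a pregnancy test administered at each testing visit", unless taking part only remotely.

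**One partner stops training.** For the Exercising Together arm, section 8.0 says: "Data will be continued to be collected on the other partner and they will be allowed to continue in the exercise program".

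**Analysis.** Section 13.0 (Analysis Plan) plans an ITT analysis of all participants whatever their adherence, fitted by maximum likelihood, which it calls unbiased under MCAR or MAR. It also plans a review of missing-data patterns, tracking of recurrence and adherence, and a completers analysis defined by attendance of at least 50%. If attrition is high and missingness is not ignorable, the same analyses proceed with more cautious conclusions. No sensitivity analysis for departures from MAR is named.

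**The concern.** The stop rule is a decision by the investigator, not a refusal by the participant. It can remove someone who is willing to answer surveys and is still training in the assigned arm. Such events are plausibly related to what the trial measures. A metastatic diagnosis or new health problem may change mood, fear of recurrence, symptoms and the couple's relationship. Symptom incongruence, one of the primary outcome measures, needs ratings from both members, so withdrawing one member ends it for that couple.

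The ITT model can still be fitted to the retained data. After these events, however, it assumes that the unseen outcomes follow what the observed ones predict, and that assumption is hard to defend here. The planned checks do not test it: observed data cannot separate MAR from non-ignorable missingness, and the completers analysis selects on attendance.

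**Working it through.** **1. The plan's own figure.** Section 13.0 needs 264 analysable couples and allows 10% attrition: 264 / (1 - 0.10) = 293.3, rounded up to 294, as stated. With even allocation, 294 / 3 = 98 couples per arm. The allowance covers loss from all causes. It protects precision and does nothing about bias.

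**2. The two rules side by side.**
- If the no-metastasis criterion applies after randomisation, section 8.0 ends data collection at diagnosis, and section 3.0 then has no later data to treat separately.
- If section 3.0 is a specific exception, the two rules are compatible. The documents do not state this.

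**3. Which criteria apply after randomisation.** Eligibility is scheduled only at screening and several criteria are dated to enrolment, which suggests entry criteria. The repeated pregnancy test points the other way. Applying the whole list cannot be intended: section 5.0 requires fewer than 2 strength sessions a week, while section 3.0 asks every arm to train on 2 days a week, so compliance itself would make participants ineligible. The rule must cover some subset of the criteria, and that subset is not given.

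**4. What unseen outcomes could do.** Let p be the fraction unobserved after an event and d the amount, in SD, by which the unseen values differ from what the model predicts. Then

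bias in the arm contrast = p1 × d1 - p2 × d2.

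Every p and d below is assumed; the documents give none. A fraction of 5% is 0.05 × 98 = 4.9 couples per arm, and 10% is 9.8.

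| Assumed scenario | Calculation | Bias (SD) |
|---|---|---|
| Equal loss, equal shift | p × d - p × d | 0 |
| Loss differs by 5 points, common shift 0.4 to 0.8 | 0.05 × 0.4; 0.05 × 0.8 | 0.02 to 0.04 |
| Loss differs by 10 points, common shift 0.4 to 0.8 | 0.10 × 0.4; 0.10 × 0.8 | 0.04 to 0.08 |
| Loss 5% in each arm, shift in one arm only | 0.05 × 0.4; 0.05 × 0.8 | 0.02 to 0.04 |
| Loss 10% in each arm, shift in one arm only | 0.10 × 0.4; 0.10 × 0.8 | 0.04 to 0.08 |
| Loss 10% in each arm, shift of 1 SD in one arm only | 0.10 × 1.0 | 0.10 |

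The sign depends on which arm carries the larger product. Zero bias needs equal loss and equal shift, or values that offset each other.

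A linear-trajectory model fitted to simulated data came within 0.003 SD of these values at 12 months. It used visits at 0, 3, 6 and 12 months, random-intercept variance 0.5, slope variance 0.1 per year squared, residual variance 0.4, no true effect and one partner role. This shows that likelihood estimation does not remove a shift it cannot see. It is not evidence about this trial, because the shift was put in by assumption.

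**The case against.** **The two rules may not conflict.** A reader might infer that sections 3.0 and 8.0 flatly contradict each other. The documents do not support that. Section 8.0 is general and does not mention metastasis, while section 3.0 is specific, and a specific rule usually governs. Tracking of recurrence in section 13.0 fits that reading. What stands is that the relation is unwritten and staff could apply either rule.

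**The partner criterion.** Section 5.0 asks for a survivor "Co-residing with an intimate partner or spouse who is willing to participate". It is tempting to say that section 8.0 breaks this by following one partner alone. But the clause reads as an entry criterion, and the section 8.0 paragraph concerns a partner who stops training. It shows no contradiction.

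**Loss by arm.** Continued follow-up of the other partner is written only for Exercising Together. A reader might infer unequal loss, or bias towards one arm. One stated rule shows neither.

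**Not all loss is avoidable.** Section 5.0 excludes people whose cognitive difficulties prevent them from answering surveys or giving consent. Someone who becomes ineligible in that way cannot properly continue. This stands, and the fix allows for it.

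**The illustration is limited.** It treats one partner role and a 12-month contrast, whereas section 13.0 models both partners jointly and tests slopes. A continuing partner's data might reduce the bias; this was not examined. Section 13.0 does not define the metric of its d = 0.40, so the values above should not be expressed as a share of it.

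**Sensitivity analysis.** Its absence concerns all attrition, not only the stop rule, and contradicts nothing in the plan. Section 13.0 does recognise non-ignorable missingness. Cautious wording, however, does not show how far the result depends on MAR.

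**Conclusion.** The point holds as a cheap improvement to a stated rule. As written, section 8.0 creates missing outcomes that are partly avoidable and may be related to outcome, and section 13.0 has no analysis that tests the resulting reliance on MAR. Sections 3.0 and 8.0 must be reconciled.

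The size and direction of any bias cannot be derived from the documents. The illustration runs from 0 to 0.10 SD on assumed inputs, and its top value needs the full 10% allowance in each arm to be outcome-related, with a 1 SD shift in one arm only. The effect may well be small: the pilot reported 100% retention (section 1.0), and the number of participants the rule would affect is not given. The stronger inference that the ITT analysis is invalid is not supported, since data before withdrawal can still be analysed.

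**What to change.** 1. In all three arms, replace the stop rule in section 8.0 with continued online surveys at 3, 6 and 12 months for every randomised participant who has not withdrawn consent and remains able to consent and respond, unless the IRB stops the study. Leave physical tests to the protocol's own safety criteria.
2. Include these data as randomised in the ITT model. Report the separate handling of post-metastasis data from section 3.0 alongside it.
3. Pre-specify one sensitivity analysis for departures from MAR, for example a pattern-mixture shift applied to missing post-event values and varied by arm.
4. State which eligibility criteria apply after randomisation, and how sections 3.0 and 8.0 relate for metastatic disease.

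**Cost.** Protocol and consent wording, a few extra surveys and slightly more analysis; the sample size does not change. Follow-up surveys are already online, and the primary outcome measures are all collected by survey (section 3.0). New wording is needed because section 8.0 foresees off-study questionnaires only later: such data "may be collected after this 12-month period, when a participant is off study, using IRB-approved language".

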### **Measures and Data Collection**

Outcomes data will be collected at 0 (baseline, just prior to randomization), 3 (mid-intervention), 6 (post-intervention), and 12 months (6 mos. after completion of the intervention (follow-up)). Written surveys are completed on a computer at the testing facility at baseline and online for follow-up visits. All measures are completed by both members of the couple at each wave.

Primary Outcome Measure:

1. Dyadic coping

Measured by the Relationship Focused Coping Scale to assess the degree with which couples practice active engagement and protective buffering using questions on a scale from 1 (never) to 5 (very often).

[Time Frame: 0 baseline (just prior to randomization), 3, 6, and 12 months]

2. Emotional intimacy

Measured by the Dyadic Adjustment Scale (DAS) to assess each partner's satisfaction with their relationship by answering questions on a 6-point scale ranging from 1(always agree) to 6 (always disagree).

[Time Frame: 0 baseline (just prior to randomization), 3, 6, and 12 months]

3. Physical intimacy

Measured by the Physical Intimacy Behavior scale which asks participants the frequency that they engage in, initiate, and avoid intimate behaviors using questions on a scale from 1 (none of the time) to 4 (most or all of the time).

[Time Frame: 0 baseline (just prior to randomization), 3, 6, and 12 months]

4. Concealment of symptoms

Measured by the Emotional-Intimacy Disruptive Behavior Scale. Patients report the extent to which they engage in 8 behaviors using a scale from 1 (rarely or none of the time) to 4 (most or all of the time).

[Time Frame: 0 baseline (just prior to randomization), 3, 6, and 12 months]

5. Symptom incongruence

Measured by the degree of agreement between the survivor and spouse/partner ratings of the survivor's pain, fatigue and physical function in the past week using the following instruments: the Brief Pain Inventory (BPI) to measure pain intensity and pain interference, Functional Assessment in Chronic Illness Therapy (FACIT) fatigue survey to measure fatigue, and perceived physical function using a subscale of the SF-36 medical outcomes survey (all described below).

[Time Frame: 0 baseline (just prior to randomization), 3, 6, and 12 months]

Secondary Outcome Measure:

6. Body composition

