
### Analysis Plan

Standard descriptive statistics/graphics will be used to check for any departures from statistical assumptions (e.g., normality, outliers, etc.).[108] We will examine dropout and patterns of missing data to determine mechanisms (MCAR, MAR, or not ignorable). In the case of data missing MCAR or MAR, model-based maximum likelihood estimation available in the MLM approach will allow unbiased parameter estimation using all available data (i.e., missing data is handled efficiently

with no loss of information). If the rate of attrition is high and missing data is not ignorable, we will continue with the planned analyses but temper our conclusions. For each aim, we will conduct intention-to-treat (ITT) and completers only analyses. ITT analyses will include all participants regardless of adherence to exercise regimen. Based on median attendance data from our prior trials, completers will be defined as participating in 50% or more of the scheduled exercise sessions. We will track medical treatment changes, cancer recurrence, and adherence to exercise. Age, comorbidities and time since diagnosis will be considered as covariates in all analyses. All analyses will be conducted in R and HLM statistical software packages (Aim 4 will be conducted using MPlus v7.2).

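### In the Exercising Together arm, stopping exercise is equated with withdrawal and further data collection is promised only for the other partner, which conflicts with the intention-to-treat plan

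*Combined protocol and SAP*

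**What the plan says.** The paragraph at issue is in Section 8.0, Follow up tests and procedures, and is headed "Drop out of one exercise partner in Exercising Together arm". It opens "If one partner of a couple is unable or unwilling to continue exercise training, any data collected on them prior to their withdrawal", and the sentence ends by saying that such data will be used in the research. It continues: "Data will be continued to be collected on the other partner and they will be allowed to continue in the exercise program". The remaining partner's programme may then be adapted for exercising alone.

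The same section has three rules that are not tied to an arm:

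- On leaving the study: "When participants drop out of the research their data will be retained for analysis".
- On loss of eligibility: "If a participant becomes ineligible during the study s/he will be withdrawn by the investigator and data will no" (the sentence runs over a page break and says that collection ends).
- On withdrawal by the investigator, one ground being "if he/she does not follow the study rules".

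Two statements elsewhere set the measurement and analysis intention. Section 3.0, Measures and Data Collection: "All measures are completed by both members of the couple at each wave". Section 13.0, Analysis Plan: "ITT analyses will include all participants regardless of adherence to exercise regimen". The Analysis Plan relies on maximum likelihood when data are missing completely at random or at random. If attrition is high and missingness is not ignorable, it keeps the same analyses and draws more cautious conclusions.

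**The concern.** The trigger in the Arm 1 paragraph is stopping the intervention, not refusing further data collection. A participant may give up the classes and still be willing to answer an online survey. A coordinator who reads that paragraph would probably stop contacting that person, because the event is called a withdrawal and only the other partner is named for continued collection.

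Three things are at stake. First, an intention-to-treat analysis that disregards adherence needs outcomes from people who stopped. Second, the rule is written for the experimental arm alone, so follow-up after stopping could differ between randomized arms. Third, the primary outcomes are relationship measures, and the Arm 1 programme consists of working with one's partner. Unwillingness to go on could be linked to those outcomes, in which case the missing values would not be ignorable. Symptom incongruence, one of the primary outcomes, compares the two partners' ratings, so later occasions would have no directly observed gap once one partner is no longer assessed.

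**Working it through.** **Step 1: the passages side by side.**

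| Question | Arm 1 paragraph, Section 8.0 | Elsewhere |
|---|---|---|
| What event? | Stopping exercise, then called withdrawal | Section 8.0 has a separate sentence on leaving the research |
| Stopped partner's later data? | Not mentioned; only earlier data are said to be used | Section 3.0: both members, every time point. Section 13.0: everyone, whatever the adherence |
| Other partner's later data? | Collected | Same |
| Arms covered? | Exercising Together only | No rule on stopping exercise in Arms 2 and 3; the general rules cover all arms |

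Section 8.0 treats leaving the research as its own event, so the Arm 1 paragraph reads most naturally as being about people who stop exercising. An explicit end to data collection appears only for participants who become ineligible. For the stopped partner, the end of assessment is implied by what the paragraph omits.

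**Step 2: the plan's own figures.** Section 13.0, Power and Sample Size, needs 264 couples and allows 10% attrition. 264 / (1 − 0.10) = 293.3, rounded up to 294, so the stated number is reproduced. 294 / 3 = 98 couples per arm, or 196 people in Arm 1. The attrition figures quoted there from earlier trials are 0% and 6%.

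**Step 3: illustrative size.** Let f be the fraction of Arm 1 participants who stop and are no longer measured, taken as equal in survivors and partners. Let k be how much worse their unobserved outcomes are, in SD, than the likelihood model would predict from the data it does have. The documents give neither. The Arm 1 mean is then too favourable by f × k.

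- f = 5%, k = 0.25: 0.05 × 0.25 = 0.0125 SD.
- f = 6%, k = 0.5: 0.06 × 0.5 = 0.03 SD.
- f = 10%, k = 0.5: 0.10 × 0.5 = 0.05 SD.

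A simulation checked the formula (four visits, 98 per arm, values lost from month 6, random-intercept mixed model). It gave 0.038 (SE 0.009) where 0.05 was expected. In a deliberately extreme case (f = 20%, k = 1.0) it gave 0.203 (SE 0.011) where 0.20 was expected.

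**Step 4: effect on the test.** Assume a simple two-arm comparison at two-sided 0.05; the plan states no alpha. With f = 10% and k = 0.5, the SE is √(1/(98 × 0.90) + 1/98) = 0.147, and the shift is 0.05 / 0.147 = 0.34 SE. Type I error becomes about 6.3%. With f = 6% and k = 0.5 it is about 5.5%.

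**Step 5: incongruence.** 5-10% of 196 people is about 10-20 people. If each belongs to a different couple, 10-20 of the 98 Arm 1 couples would have no directly observed gap after the stop. Their earlier occasions remain in the model.

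**The case against.** The best defence is that the paragraph never says assessment stops. Saying that earlier data will be used is a statement about retention, and where the authors meant collection to end, for ineligible participants, they said so. The words for dropping out and withdrawal also echo the general sentence on leaving the research, so the paragraph may concern partners who leave the study. Any wording on withdrawal in the consent form is not in the material reviewed. The arm-specific heading has an operational reason: only Arm 1 uses paired roles and tandem exercises, so only there does losing a partner disrupt the other's programme.

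Much of this stands, and it rules out several stronger readings:

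- A reader might infer that the plan states a rule of no further follow-up. It does not; that is an implication.
- A reader might infer that people who stop are lost in Arm 1 but measured in Arms 2 and 3. The statements on both partners and on intention to treat apply to all three arms, and the documents say nothing specific about people who stop in Arms 2 and 3. Differential follow-up is a risk, not a documented fact.
- A reader might infer that people stop for reasons tied to the primary outcomes, so that the bias favours Exercising Together. The documents do not show this, and inability to continue also covers illness and injury.
- A reader might infer that the couple drops out of the incongruence analysis. It keeps its earlier occasions, and the Section 13.0 model uses all available data.
- A reader might assume larger inputs, such as 15% stopping. That exceeds the plan's 10% attrition allowance.

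What the defence does not remove is the drafting defect. Stopping exercise and leaving assessment are not separated, and only the other partner is promised further data collection.

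**Conclusion.** The concern holds as a conflict between passages with a risk attached. Followed in its natural sense, the Arm 1 paragraph would produce avoidable missing outcomes after stopping. These could differ by arm and be non-ignorable, and the analysis plan has no sensitivity analysis for that case.

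The likely size is small to moderate: about 0.01-0.05 SD in the Arm 1 mean. This rests on assumed inputs (5-10% stopping, outcomes 0.25-0.5 SD worse than predicted) and on all of those participants being lost to assessment. If only one partner stops in 10% of Arm 1 couples, that is about 10 of 196 people, or 5%, and at 0.5 SD the shift averaged over both roles is 0.05 × 0.5 = 0.025 SD. Against the design effect of d = 0.40, 0.05 SD would be 0.05 / 0.40 = 12.5%. That ratio is only indicative, because the plan defines d on change over time. The sign of the bias is plausible, not established. The point merits correction mainly because the remedy is cheap and outcomes not collected on time generally cannot be recovered later.

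**What to change.** Reconcile the Arm 1 paragraph in Section 8.0 with Sections 3.0 and 13.0 by one rule covering all three arms. For example: a participant who stops exercise training remains in all scheduled surveys and testing at 3, 6 and 12 months unless he or she withdraws consent for data collection, and the same applies to the other partner. Record stopping exercise and leaving data collection as separate dated events with reasons, tabulated by arm and by role. For outcomes that are still missing, a delta-adjusted sensitivity analysis would be a useful companion, but it does not replace collecting the data.

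The cost is a short amendment. The primary outcomes are questionnaires, follow-up surveys are already online, and part of the testing can be done remotely. The sample size is unaffected, and the change concerns data collection only, not who may exercise or how. The downside is some extra contact with people who have stopped exercising, who may decline.
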